7.3 LOST TO FOLLOW-UP

A participant will be considered lost to follow-up if they are no longer a member of the clinical program, or if they fail to respond to 3 consecutive months of texting, or 3 monthly assessments in a row, and study staff are unable to contact the participant after at least 3 attempts.

The following actions will be taken if a participant fails to respond:

- The site will attempt to contact the participant, counsel the participant on the importance of maintaining the assigned schedule and ascertain if the participant wishes to and/or should continue the study.
- Before a participant is deemed lost to follow-up, the investigator or designee will make every effort to regain contact with the participant (where possible, 3 telephone calls and, if necessary, a certified letter to the participant's last known mailing address or local equivalent methods). These contact attempts will be documented in the participant's study file.
- Should the participant continue to be unreachable, he or she will be considered to have withdrawn from the study with a primary reason of lost to follow-up.

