4 STUDY DESIGN

4.1 OVERALL DESIGN

This is a pilot randomized, controlled clinical trial to establish the intervention protocol's feasibility, acceptability, and fidelity, as well as preliminary effect size data. All study participants will undergo informed consent including authorization to view the child's medical record and consent to participate in action planning, health coaching, and weekly text message surveillance.

To participate in this study, a patient must be cared for at one of two sites (University of Wisconsin/American Family Children's Hospital or UCLA/Mattel Children's Hospital) in their complex care or cerebral palsy clinical programs, and meet study inclusion criteria, which include presence of severe cerebral palsy and respiratory care needs (see **Section 5, Study Population** for details).

Following an intervention adaptation phase consisting of formative data from focus groups with primary caregivers, clinical teams and a group of national experts, this phase will employ the evidence-based Replicating Effective Program's framework for intervention adaptation and the Patient-Centered Outcomes Research Institute's standards for improving research of complex health interventions. The previously efficacious PACT (Plans for Action and Care Transitions) intervention has been adapted to prevent severe respiratory illness in children with severe cerebral palsy, and to increased dose triggers from text messages indicating a family's low confidence for their child to avoid a hospitalization in real-time. In addition, the Core Functions (standard components required for integrity) and Forms (the tailored activities to carry out the Core Functions) have been delineated. The adapted intervention is called RE-PACT, or Respiratory Exacerbation Plans for Action and Care Transitions.

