4.2 SCIENTIFIC RATIONALE FOR STUDY DESIGN

Rational for the study design. Conducting this pilot study will provide a high degree of certainty that the final RE-PACT protocol is feasible, acceptable and can be delivered with fidelity. This is a critical approach to designing interventions that can be integrated in diverse, real-world, settings and sustained.

Using an RCT design (i.e., with a control group who do not receive intervention) is necessary to establish effect sizes needed to adequately power an efficacy trial. The findings from this study will allow precise estimation of effect sizes to conduct a fully powered, multisite hybrid Type 2 effectiveness-implementation RCT.

Rationale for the type and selection of control conditions. The control group will be randomly assigned, allowing the study team to conclude that endpoint differences between each group are most likely due to the intervention itself.

Potential problems associated with the control group. The control group may have pre-existing respiratory action plans created during routine clinical care. In addition, the coach may have difficulty avoiding contaminating the control group by inadvertently conducting coaching activities to those not assigned to the intervention group. This risk will be minimized since action plans using the study protocol will only happen for intervention subjects, and coaching is triggered only through mHealth text responses and texting will only be set up for those assigned to the intervention.

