5.5 STRATEGIES FOR RECRUITMENT AND RETENTION

Recruitment

We will recruit caregivers of children with severe CP between 0-17 years old. We will recruit a total of n=90 participants (n=45 at each site) divided across 3 waves. In each wave, there is a 1-2 month enrollment period. We anticipate approximately 80% of those screened will enroll, requiring approximately 110 individuals to be screened.

Potential participants will be identified by reviewing the clinic registries and/or EHR data using diagnostic codes for CP (ICD-10 G80-83), which contain detailed information about children and their diagnoses. We will send an “opt-out” letter that alerts families that a research study is being conducted and their child may be eligible, with a contact number to call if they wish to opt out of the research or if they wish to receive additional information or have any questions. Potentially eligible caregivers will be contacted by phone to screen for eligibility and interest.

If the research team is not notified that a family wishes to opt-out the research, the study research personnel will attempt to call the families (or meet them at an upcoming visit) to complete screening, informed consent, baseline questionnaires and random group assignment. Eligibility criteria for caregivers are detailed in **Study Population, Section 5.1-5.2**, and include being self-identified English- or Spanish-speaking caregivers of children with severe CP who have respiratory needs. CP status and additional eligibility criteria will be determined with a reliable and valid parent questionnaire and screener conducted at the beginning of initial phone contact.

Retention and Incentives

Study participants in this pilot RCT will be contacted at baseline (enrollment), monthly (for intervention subjects), and at 6 months (intervention and control groups). While we expect some degree of attrition will be inevitable, we will work to minimize attrition by sending regular follow-up post cards and phone calls requesting updates in contact information and also confirming or updating contact information when child medical records are reviewed. Moreover, participants will receive \$100 on study entry and exit.

Inclusion of Women and Minorities

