9.2 SAMPLE SIZE DETERMINATION

We will enroll a total of 90 participants. Wave 1 will contain 10 participants (5 UW, 5 UCLA); Wave 2 will contain 20 participants (10 UW, 10 UCLA); Wave 3 will contain 60 participants (30 UW, 30 UCLA). Based on this team's preliminary work, eligible children average one severe respiratory illness per year and we estimate 50% of participants will experience at least one respiratory illness during the period of enrollment. We expect to be able to maintain contact and collect data from ≥90% of the participants at the final follow-up, evenly divided between intervention and control groups. We assume this sample will not be powered to establish the efficacy of the intervention; however, it will provide a sufficient sample to determine feasibility and estimate effect sizes which will be used for power calculations in the future large RCT. The following table shows the attainable power levels for detecting various differences in severe respiratory illness rates (primary clinical outcome) between study arms at the two-sided 0.05 significance level, based on a NB regression model with an overdispersion parameter of $\phi=1.0$.

Attainable power levels for detecting differences in severe respiratory illness rates between arms at the two-sided 0.05 significance level based on a NB regression model, assuming a sample size of 45 subjects per arm with a missing value rate of 10% or less.

Relative Risk (RR)	Number of severe respiratory illnesses in intervention arm over 6-month Follow-up period				
	5	10	15	20	25

(Control vs. Intervention) ($\lambda=0.02$)*	($\lambda=0.40$)*	($\lambda=0.06$)*	($\lambda=0.08$)*	($\lambda=0.10$)*
3.0	19%	29%	38%	45%
4.0	31%	41%	59%	68%
5.0	42%	62%	74%	83%

*Severe respiratory illness rate per patient-month

Hence, large effect sizes with RRs ranging between 3.0-5.0 for comparing the severe respiratory illness rates between study arms will be detected with 19-88% power at the two-sided 0.05 significance level.

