Secondary clinical outcomes include total hospital days during severe respiratory illness, numbers of systemic steroid courses, systemic antibiotic courses, respiratory ED visits and death. The numbers of systemic steroid courses, systemic antibiotic courses, and respiratory ED visits over the 6 months follow-up period will be analyzed using NB regression analyses in a similar fashion as described above for the primary outcome. Observed effect sizes will be reported along with the corresponding 95% confidence intervals. The presence/absence of systemic steroid courses, systemic antibiotic courses, and respiratory ED visits will be documented at the monthly assessments and longitudinal changes within and between study arms will be analyzed using generalized linear mixed effects modeling with a logit link function and patient specific random effects. The total number of hospital days over the 6 months follow-up period will be analyzed using analysis of variance (ANOVA) with study site as stratification factor. In a secondary analysis, analysis of covariance (ANCOVA) will be performed where clinical and demographic baseline characteristic will be included as covariates and the lasso method will be used to identify a parsimonious

model. Longitudinal changes in the number of hospital days per hospitalization will be analyzed using a normal mixture linear mixed effects model with patient specific random effects. The normal mixture component will be included in the model to capture the probabilities of a hospitalization at the monthly follow-up. Parameter estimation will be performed using the Expectation-Maximization algorithm which is the standard method for parameter estimation of mixture models.

Missing values, e.g., due to loss of follow-up, missing monthly visits, will be evaluated by conducting a sensitivity analysis comparing the results obtained from the complete case analysis to the results obtained by imputation-based analyses. Specifically, multiple imputation (MI) will be used to impute missing values of primary and secondary clinical outcomes. For monotonic missing values data structures, we will use regression-based MI techniques. For non-monotonic missing value data structure, on the other hand, we will use Markov Chain Monte Carlo based imputation techniques.

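### Section 7.3 treats loss of contact as withdrawal from the study and does not say that chart follow-up continues, so observable clinical outcomes can be lost, and differently by arm

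*Combined protocol and SAP*

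**What the plan says.** - **Trigger (7.3).** Participants are lost to follow-up if they leave the clinical program, or if they "fail to respond to 3 consecutive months of texting, or 3 monthly assessments in a row" and staff cannot reach them after at least three attempts.
- **Consequence (7.3).** If still unreachable, "he or she will be considered to have withdrawn from the study with a primary reason of lost to follow-up". Section 7.2 also lists inability to contact as a ground for discontinuing a participant from the study.
- **Contrast (7.1).** Someone who stops the intervention but not the study stays in all later assessments. Section 7.3 has no equivalent.
- **Record access (4.1).** All participants give "informed consent including authorization to view the child's medical record". Section 10.1.1.2 confirms this, lets parents decline parts of the study, and lets them revoke consent.
- **Data sources.** Section 4.1 names questionnaire and record review in both arms, section 5.5 names parent report and record review for child-level data, and section 8.1 mentions monthly chart reviews.
- **Missing data.** Section 9.2 states "We expect to be able to maintain contact and collect data from" at least 90% of participants, evenly divided between arms; its power table allows 10% or less missing. Section 9.4.3 says "Missing values, e.g., due to loss of follow-up, missing monthly visits, will be evaluated by conducting a sensitivity analysis", comparing complete cases with multiple imputation of the clinical outcomes.
- **Population (9.3).** Intention-to-treat.

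**The concern.** Losing contact with a caregiver is not the same as losing sight of the child's outcome. The primary clinical outcome is an admission with a qualifying respiratory discharge diagnosis. For a child who remains a patient of the program, staff can look for that in a chart they are already authorised to read. By placing an unreachable family outside the study, section 7.3 invites the team to stop looking.

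Two things are at stake. One is precision of the effect size, which is the secondary objective and is meant to size a later trial. The other is selective loss: a caregiver may fall silent because of a crisis, an admission or a death, or because the child is well and the texts seem pointless. Because the triggers depend on contacts that only one arm receives, the loss need not balance between arms.

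**Working it through.** **1. Which arm can meet the triggers?** Section 4.2 says "texting will only be set up for those assigned to the intervention". Section 1.3 lists monthly study assessments under the intervention arm only, and section 5.5 has controls contacted at baseline and month 6 only. On these sections a control family cannot miss three months of texts or three monthly assessments. Controls can be missing at the exit assessment or leave the program, but they cannot be declared lost in mid-course for non-response. Section 9.2 nevertheless assumes even retention.

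**2. The plan's own figure.** Section 9.2 gives 19–88% power for 45 per arm with up to 10% missing. A Wald test for negative binomial rates with 40 per arm, overdispersion 1, pooled null variance and a mean equal to the monthly rate gives 19.3% to 88.1%, and comes within 2 points of 11 of the 12 legible cells. So the 10% loss appears to be built in. With six months of exposure the table is not reproduced (first cell 49–62% against 19%). That mismatch is a separate matter and does not affect this point.

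**3. Precision.** Inputs from section 9.2: one illness per child-year, so μ = 0.5 over six months; φ = 1; 45 per arm. Both arms are set at 0.5. For scale, the full 10% is lost: 9 of 90, or 4.5 per arm.

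- Information per child on the log rate = μ/(1 + φμ): 0.5/1.5 = 0.333 for six months; 0.25/1.25 = 0.200 for three.
- SE(log RR) = √(2/I), where I is the information per arm.

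| Case | I per arm | SE | 95% CI factor, exp(1.96·SE) |
|---|---|---|---|
| Lost children dropped whole | 40.5 × 0.333 = 13.5 | 0.385 | 2.13 |
| Each contributes 3 months (assumed) | 13.5 + 4.5 × 0.200 = 14.4 | 0.373 | 2.08 |
| All followed by chart | 45 × 0.333 = 15.0 | 0.365 | 2.05 |

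The information gain is 15.0/13.5 = 1.11 or 15.0/14.4 = 1.04. In person-time, 54 of 540 months (10%) or 27 of 540 (5%) are at stake. With an assumed intervention/control RR of 0.6 and whole-child loss, power moves only from 22.4% to 24.4%.

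**4. Selective loss (illustration only).** Let a fraction p of the intervention arm be dropped whole, with m times the illness rate of those retained, and no selective loss in controls. Then observed RR = true RR / [1 + (m − 1)p]. For an assumed true RR of 0.6:

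| m | p = 0.10 (4.5 of 45) | p = 0.20 (all 9 of 45) |
|---|---|---|
| 0 | 0.67 | 0.75 |
| 0.5 | 0.63 | 0.67 |
| 2 | 0.55 | 0.50 |
| 3 | 0.50 | 0.43 |

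The error can go either way. It would be smaller if person-time before the loss is kept, which section 9.4.3 does not specify.

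**The case against.** **Silence is not a stop order.** The documents never say that chart review ends at loss of contact; a reader might infer that it does. This stands: it is an inference. It is supported by the contrast between 7.1 and 7.3, and by 9.4.3 naming loss of follow-up as a cause of missing values and planning to impute clinical outcomes. For the same reason it is too strong to say that intention-to-treat is broken.

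**Charts are not the only source.** Sections 4.1 and 5.5 include questionnaire or parent report. Admissions or prescriptions elsewhere may not appear in the site's records and would be counted as zero, mainly in the intervention arm. This stands and shapes the fix.

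**Size.** A reader might infer that a tenth of the data is needlessly lost, or that 11% of the information is recoverable. The documents do not support this. The 10% covers all missing data, including active withdrawal and program leavers, and the 11% requires dropping whole children although the outcome is illnesses per person-month.

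**Arm.** A reader might also infer that losses pile up among controls, who have no scheduled contact between baseline and month 6. With no true effect, losing 2 intervention and 7 control families at 2 to 3 times the illness rate would give an RR of 1.11 to 1.20. But 7.3's non-response triggers do not reach controls. Section 1.1 does mention monthly assessments without naming an arm; sections 1.3 and 5.5 limit them to the intervention arm.

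**Importance.** The primary objective is feasibility, and the effect size is declared underpowered. Multiple imputation is planned, but only as a sensitivity analysis, and it cannot repair outcome-dependent loss without further assumptions.

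**Conclusion.** The concern holds in a limited form. As written, the plan classes unreachable families as withdrawn, does not provide for continued chart follow-up, and expects clinical outcomes to be missing as a result, although authorised records could supply many of them for children still in the program. The triggers work in one arm only, so follow-up can be removed differentially; the direction of any bias cannot be stated from the documents.

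The precision gain is small: about 5% in the SE at most under the planned allowance, and about 2% if three months of each lost child's follow-up are kept. The case for change rests on selective loss, whose size depends on assumed multipliers and splits, and on an unknown number of families. The conclusion excludes families who leave the program or revoke authorisation. It assumes that the consent wording, which was not available for this review, allows chart review after loss of contact.

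**What to change.** - **7.3, with 7.2 aligned.** Replace the withdrawal wording along these lines: *a participant who cannot be reached is recorded as lost to contact for questionnaires and intervention activities; unless the caregiver revokes authorisation, chart abstraction of all clinical endpoints continues to month 6.* Confirm first that the consent wording covers this.
- **Section 3.** Keep counting these families as passive drop-out against the under-10% target, so that the acceptability endpoint is unchanged.
- **9.4.3.** Use chart-derived outcomes for these children in the intention-to-treat analysis. Report missingness and outcome source by arm. Add a sensitivity analysis that treats their person-time after loss of contact as missing.

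**Cost.** Protocol wording, a check of the consent form, and chart abstraction by existing staff: nine children if the whole 10% allowance were unreachable families. The downside is possible under-capture of admissions outside the site's records, which the source reporting and sensitivity analysis would expose.

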8 STUDY ASSESSMENTS AND PROCEDURES

8.1 ENDPOINT AND OTHER NON-SAFETY ASSESSMENTS

Screening, Eligibility and Enrollment Procedures

Using clinic registry or EHR data (see **Section 5, Strategies for Recruitment and Retention**), all children with known or suspected severe CP, up to age 17 years will be identified. After sharing introductions with these identified individuals by mail and telephone, trained research personnel will begin approaching potential participants using a standardized recruitment and screening script (for use in person, virtually or by telephone) to screen eligibility and interest. The eligible participant pool will be assembled up to 3 months prior to beginning wave 1 enrollment. Screening will be used during each trial wave's recruitment period until the recruitment target is reached. Randomization/enrollment will occur at the same time as screening but can be completed up to 1 month after screening if families need additional time.

The screening questionnaires will confirm:

- Caregivers: are at least 18 years of age, are the primary caregiver to candidate child (child criteria below), speak English or Spanish well enough to be interviewed, have a phone capable of sending/receiving text messages, and are willing to send/receive text messages on their device.
 - These measures are self-reported.
- Children: are 0-17 years of age, have Gross Motor Function Classification System Level IV or V Cerebral Palsy, are cared for by respiratory specialist or receive daily respiratory treatments (oxygen, ventilation, airway clearance device, medications).
 - The Gross Motor Function Classification System (GMFCS) levels are determined by parent-report using a validated parent questionnaire.⁷⁴ The family chooses the most accurate description of their child, and this corresponds directly to their GMFCS level based on their age.
 - Need for specialty respiratory care and/or respiratory treatments is self-reported

Screening procedures continue until someone is deemed ineligible. Once deemed ineligible, the individual is thanked, and the interaction concludes. Screening results and reasons for ineligibility will be retained by study personnel.

Study Endpoint Measures and Assessment Procedures

Primary Study Endpoints - Feasibility, Acceptability, Fidelity: The specific measures and pre-specified definitions of success are listed in **Section 3**. These measures will be summarized between each of the three waves with protocol adjustments made for any measures below the definition of success.

Clinical Endpoints:

- Primary clinical outcome is severe respiratory illness, defined as respiratory diagnosis requiring hospitalization. Respiratory diagnosis includes discharge diagnosis of any of the following: asthma, pneumonia

(community or hospital acquired), bronchiolitis, influenza, upper or lower respiratory tract infection, tracheitis, aspiration pneumonia/pneumonitis, chronic lung disease, respiratory failure.¹²⁰ Field-testing assessment of this endpoint with trained research personnel at study sites demonstrated inter-rater reliability (Kappa) > 0.9.

- Secondary outcomes include: total hospital days during severe respiratory illness, numbers of systemic steroid courses, systemic antibiotic courses, respiratory ED visits, and death. Systemic corticosteroid course is defined by oral or parenteral corticosteroid prescribed for respiratory diagnosis, including hydrocortisone, prednisone, prednisolone, or methylprednisolone at least 1 mg/kg/day (or 30 mg/day) x minimum 3 days, or dexamethasone at least 0.15 mg/kg/day (or 10 mg/day) x 1 or more days. Physiologic or stress replacement doses in adrenal insufficiency are excluded. Systemic antibiotic course is defined by oral or parenteral antibiotics prescribed for respiratory diagnosis x minimum 3 days. The specific antibiotics are derived from IDSA pediatric pneumonia guidelines¹²¹ and published literature.¹²² Respiratory ED visits are any ED visits not resulting in admission and have a discharge respiratory diagnosis.

Additional Assessment Measures:

MEASURES	SOURCE	MEASURE DETAIL
Covariates		
Child and Caregiver Demographics	Survey	Child: age, gender, primary language, race/ethnicity, payer, family structure Caregiver: relationship, age, gender, language, race/ethnicity, education, health literacy, ¹¹⁴ income, rurality
Confounders		
Child Clinical Characteristics	Electronic health record	Organ systems affected by chronic conditions, subspecialists in past year, medical technologies used (e.g., tracheostomy, gastrostomy, etc.), duration of enrollment clinical program, numbers of ED visits and hospitalizations in past year, and respiratory treatments at time of enrollment (medications and devices)
Caregiver Strain	Survey	Caregiver Strain Questionnaire (CGSQ); ¹¹⁵ – mean global, objective, subjective scale scores Mental health (PHQ2) ¹¹⁶
Theory / Mechanism		
Capability	Survey	Family Caregiver Activation in Transition Measure (FCAT) ¹¹⁷ – mean composite score Caregiver General Self-Efficacy Scale (GSES) ¹¹⁸ – mean composite score
Opportunity	Survey	Family Experiences with Care Coordination (FECC) ¹¹⁹ - % top-box score for selected items
Motivation	Text logs	Confidence Responses mHealth texting (weekly score 1 through 10)

Assessment Procedures. Feasibility, acceptability and fidelity endpoint data will be collected during each of the three waves by research personnel reviewing study logs, conducting monthly chart reviews, and

administering surveys (by telephone, in person, or sending electronic self-administered links) with caregivers randomized to intervention. For active control groups participants, feasibility of assessments will be evaluated by completion rates at study exit. Caregiver and child measures above will be recorded at baseline, endpoints will be recorded at study exit (6 months after T0). Caregiving measures, which may change as a result of the intervention, will be collected at baseline and study exit. In addition, intervention and active control caregivers will be debriefed at study exit on their experiences in the study, and asked for feedback on the strengths, weaknesses and any concerns about the protocol. Between each wave and after the third wave, clinical teams at each site will be debriefed on strengths, weaknesses, and concerns about the protocol.

Reliability of Assessment Measures. The CP GMFCS measures and all the caregiving measures have been well-documented as reliable in the literature.^{11,74,115-119} We have separately established the reliability of identifying respiratory illnesses in our preliminary research (Kappa > 0.9). We will ensure reliability in data collection through direct observation, data auditing, establishing clear data dictionaries / definitions, using uniform variable definitions, and a central data repository coordinated and maintained by UW.

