5 STUDY POPULATION

5.1 INCLUSION CRITERIA

The participant is the caregiver of a child with severe cerebral palsy. Individuals must meet all of the inclusion criteria in order to be eligible to participate in the study:

Caregiver Criteria

- Be at least 18 years of age
- Primary caregiver to an eligible child (child criteria below)
- Speak English or Spanish well enough to be interviewed
- Have a phone capable of sending/receiving text messages

Child Criteria

- Ages 0-17 years
- Have Gross Motor Function Classification System level IV or V Cerebral Palsy
- Cared for by respiratory specialist or receive daily respiratory treatments (oxygen, ventilation, airway clearance device, medications)

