6 STUDY INTERVENTION(S) OR EXPERIMENTAL MANIPULATION(S)

6.1 STUDY INTERVENTION(S) OR EXPERIMENTAL MANIPULATION(S) ADMINISTRATION

6.1.1 STUDY INTERVENTION OR EXPERIMENTAL MANIPULATION DESCRIPTION

The Respiratory Exacerbation Plans for Action and Care Transitions (RE-PACT) intervention has three primary activities: (1) mHealth surveillance of parent confidence to avoid hospitalization, (2) respiratory illness action planning, and (3) just-in-time adaptive coaching response triggered by low confidence or hospitalization. The theoretical basis of the intervention includes efficacy of the initial PACT trial, and prior research on preventing hospitalizations combined with behavioral intervention theory which suggests that decisions to seek care (behaviors) are influenced by capability (family capacity), opportunity (health system and susceptibility), and motivation (confidence). Confidence is a modifiable expression of self-efficacy to achieve an outcome, i.e., to avoid hospitalization and manage (respiratory) crisis at home. In our earlier work, low confidence predicted hospitalization.

Participants randomized into the intervention will receive initial T_0 intervention activities (mHealth monitoring and respiratory action plan) by phone, at clinic, or during a hospitalization within one month of enrollment.

mHealth surveillance. Upon enrollment, families will begin receiving weekly text messages asking them to rate their confidence (1-10) for their child to avoid a hospitalization in the next month.

Action Planning. The action and format are adapted from the original PACT study, and contents include (at minimum) recognizing, describing and managing the child's known contributors to respiratory illness. In step 1, objective and subjective indicators of baseline ("green"), concerning ("yellow"), and severe ("red") statuses are defined (e.g., >2 L/min of oxygen). In step 2, the specific actions caregivers should take to manage each status are defined (e.g., increase vest, albuterol, suction to q4, use oxygen up to 4 L/min).

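### The antibiotic-course endpoint has no new-start or acute-episode condition, so standing respiratory antibiotics can count as events and dilute the arm comparison

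*Combined protocol and SAP*

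**What the plan says.** Section 8.1 lists systemic antibiotic courses among the secondary clinical outcomes and defines them thus: "Systemic antibiotic course is defined by oral or parenteral antibiotics prescribed for respiratory diagnosis x minimum 3 days". The next sentence limits the drugs: "The specific antibiotics are derived from IDSA pediatric pneumonia guidelines", together with published literature. The list itself is not reproduced.

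The steroid definition just before it is tighter. It sets dose floors and minimum durations, and adds: "Physiologic or stress replacement doses in adrenal insufficiency are excluded".

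The respiratory diagnoses accepted in Section 8.1 include asthma and end with "tracheitis, aspiration pneumonia/pneumonitis, chronic lung disease, respiratory failure", so chronic conditions are among them.

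Under Section 5.1 a child qualifies through respiratory-specialist care or through daily respiratory treatment. Medications are one kind of such treatment; antibiotics are not named. Section 8.1 also records respiratory medications and devices at enrollment, as a confounder.

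Section 9.4.3 applies negative binomial regression to "The numbers of systemic steroid courses, systemic antibiotic courses, and respiratory ED visits over the 6 months follow-up period". It also models monthly presence or absence of antibiotic courses with a logit mixed model. Section 9.4.9 uses the course count again as a mediation outcome.

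**The concern.** The count is meant to reflect treated respiratory episodes and to supply an effect size for a later trial. The rule as written is met by a prescription, a respiratory diagnosis and a duration. A child on long-term antibiotic treatment for chronic lung disease meets all three without any new illness. The rule does not say whether a renewal is a new course. In the monthly model such a child could score as positive in all six months.

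The intervention is not aimed at background prescriptions, so they would add roughly the same number of events to both arms. Equal additions to numerator and denominator move a rate ratio toward 1. The population is selected for respiratory-specialist care or daily respiratory treatment, so the question is relevant here. The steroid wording shows that the authors saw background therapy as a problem for that drug class.

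**Working it through.** The documents state no rate, effect size or power for antibiotic courses, so there is no planned figure to reproduce. What follows is an illustration on stated assumptions.

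**Inputs**
- 45 children per arm (Section 9.2).
- True acute-course ratio, intervention to control: 0.60. This is an assumption. The only 40% reduction in the documents is for hospitalizations in the earlier PACT trial (Section 2.2).
- Acute courses per control child over 6 months, r: 1.0 (assumption), with 0.5 as an alternative. The 0.5 is borrowed from the average of one severe respiratory illness per year in Section 9.2.
- Share of children on standing therapy, s: 5% to 30% (assumption), equal in both arms because of randomization.
- Counts per such child, k: 1 (counted once) or 6 (counted monthly).

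**Dilution.** Observed ratio = (0.60r + ks) / (r + ks).

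With r = 1.0 and s = 10%:
- k = 1: (0.60 + 0.10) / (1.0 + 0.10) = 0.64
- k = 6: (0.60 + 0.60) / (1.0 + 0.60) = 0.75

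| s | r = 1.0, once | r = 1.0, monthly | r = 0.5, once | r = 0.5, monthly |
|---|---|---|---|---|
| 5% | 0.62 | 0.69 | 0.64 | 0.75 |
| 10% | 0.64 | 0.75 | 0.67 | 0.82 |
| 20% | 0.67 | 0.82 | 0.71 | 0.88 |
| 30% | 0.69 | 0.86 | 0.75 | 0.91 |

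If the true ratio is 1, it stays at 1. The effect is attenuation only.

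**Chance imbalance at s = 10%.** The SD of the between-arm difference in background counts is k × √(2 × 45 × 0.1 × 0.9).
- k = 1: √8.1 = 2.8 courses
- k = 6: 6 × √8.1 = 17.1 courses

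For comparison, take the sampling SD of the difference in acute courses at r = 1.0, with dispersion 1.0 borrowed from Section 9.2. It is √(45 × [(1.0 + 1.0²) + (0.6 + 0.6²)]) = √133.2 = 11.5. Adding background counts gives:
- k = 1: √(133.2 + 8.1) = 11.9, about 3% more
- k = 6: √(133.2 + 291.6) = 20.6, about 79% more

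**On the log-ratio scale.** A simulation with r = 0.5, dispersion 1.0 and 45 per arm gave these medians and SDs:
- no background counts: ratio 0.60, SD of log ratio 0.415, |log ratio|/SD = 0.511/0.415 = 1.23
- s = 10%, counted once: 0.673, SD 0.350, 0.396/0.350 = 1.13
- s = 10%, counted monthly: 0.813, SD 0.438, 0.207/0.438 = 0.47

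On this scale the SD need not rise, because there are more events. The main loss is signal. It is small if standing therapy is counted once and large if it is counted monthly.

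**The case against.** The strongest reply is that this is a gap in wording and not a demonstrated distortion. No section mentions prophylactic antibiotics. The antibiotic list is not shown, and Section 8.1 promises clear data dictionaries that might settle the matter. The larger ratios depend on counting each renewal, which the text does not direct. Unequal baseline variables are to be adjusted for. The endpoint is one of several secondary outcomes in a pilot that expects to be underpowered.

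Most of this limits the size of the point without removing it. The list restricts by drug, not by purpose, so a listed drug given as prophylaxis still qualifies. The protocol states a rule that includes such use, so a dictionary that follows the rule would include it too. Adjustment under Section 9.4.5 is triggered by a statistically significant baseline difference, which balanced background use would not produce. Even where a standing-treatment covariate is fitted, the non-illness events stay in the outcome. The kappa above 0.9 in Section 8.1 concerns identification of respiratory illness, not antibiotic courses.

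A reader might go further and infer bias against the intervention. Study action plans are written only in that arm, and in them "the specific actions caregivers should take to manage each status are defined". Standby prescriptions written under a plan would count even if unused. Were there one per ten intervention children and none in controls, 0.60 would become (0.60 + 0.10) / 1.0 = 0.70 at r = 1.0. The documents do not support that step. The example actions in Section 6.1.1 include no antibiotic. Section 4.1 says plan content will not differ from the clinical team's recommendations. Section 4.2 accepts that controls may already have action plans, and Section 6.5 lets participants use plans made outside the study. Standby prescribing, if it happens, could happen in both arms.

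**Conclusion.** The point holds as over-inclusive wording for one secondary endpoint. Taken literally, the rule counts standing respiratory antibiotics as events. The consequence is attenuation toward 1, plus chance variation in the count difference. With 10% of children on standing therapy, a true ratio of 0.60 and 1.0 acute course per control child, the expected ratio is about 0.64 (counted once) to 0.75 (counted monthly). At 0.5 acute courses it is 0.67 to 0.82. Prevalence, acute rate and true ratio are all assumptions; if no enrolled child has standing therapy, the effect is nil.

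Bias favouring one arm is not established. The feasibility, acceptability and fidelity outcomes and the hospitalization outcome do not use this definition.

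**What to change.** In Section 8.1, change the counting rule as follows:
- A course is a listed antibiotic newly prescribed for an acute respiratory episode, keeping the existing minimum duration.
- Antibiotics already recorded as ongoing in the baseline list of respiratory treatments do not count unless changed for an acute episode.
- Renewals count as part of the same course, as does an inpatient course continued after discharge.
- The rule is applied by the same chart-based abstraction in both arms.

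Do not make the count depend on caregivers confirming that a drug was started. Section 5.5 gives monthly contact to intervention families only, so that requirement would make ascertainment differ by arm. The price is that a new prescription for an acute episode that was never taken still counts, under the same rule in both arms.

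The cost is a few sentences and a new-start field on the case report form; the baseline medication data are already collected. The downside is slightly fewer counted courses and a little more judgement in abstraction. This changes only what is counted, not how any child is treated.
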